4.3. General Statistical Methods and Data Handling

4.3.1. General Methods

All output will be incorporated into Microsoft Excel or Word files, sorted and labeled according to the International Conference on Harmonisation (ICH) recommendations, and formatted to the appropriate page size(s).

Tabulations will be produced for appropriate demographic, baseline, efficacy and safety parameters. For categorical variables, summary tabulations of the number and percentage within each category (with a category for missing data) of the parameter will be presented. For continuous variables, the mean, median, standard deviation, minimum and maximum values will be presented. Time to event data will be summarized using Kaplan-Meier Methodology using 25th, 50th (median), and 75th percentiles with associated 2-sided 95% confidence intervals, as well as percent of censored observations.

Formal statistical hypothesis testing will be performed on the primary and secondary efficacy endpoints with all tests conducted at the 1-sided, 0.025 level of significance. Summary statistics will be presented, as well as confidence intervals on selected parameters, as described in the sections below.

For all analyses, baseline will be defined as the most recent measurement prior to the date and time of the administration of active treatment with Pharyngeal Electrical Stimulation or a sham treatment. Therefore, baseline may be on the same day as the start of study treatment, but prior to the administration of the study treatment.

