4.5.3. Procedure at the second interim analysis

The second interim analysis is planned for when for when 120 patients complete their 7 day visit.

Efficacy stopping: An early efficacy stopping boundary of Z > 2.5093 (one-sided P < 0.0060) will be used for all efficacy endpoints. This boundary is the group sequential boundary derived from the Lan-DeMets O'Brien Fleming spending function at 2/3 information fraction. Early stopping for efficacy will be recommended only if both the primary endpoint and secondary endpoint cross the same boundary. If the study continues, both endpoints will be tested against the group sequential boundary 1.9929 at the final analysis in a sequential manner -- the secondary endpoint is tested if the primary endpoint reaches statistical significance -- to preserve the study-wise type 1 error rate at one-sided level 0.025.

If the study is not stopped for efficacy, the interim results will be classified into different zones depending on estimation of the conditional power on the primary endpoint and, separately, on the secondary endpoint. Based on the interim zone, one of the following actions will be recommended:

- Stop the study for futility (non-binding stop).
- Continue the study until reaching the planned 180 evaluable patients (approximately 225 enrolled).
- Continue the study and increase the sample size up to a maximum of 270 evaluable patients (approximately 338 enrolled).

Details on the boundaries of these interim zones and specific actions to be taken within these zones are deferred to a restricted Simulation Report whose circulation is limited to a core study team to include the ISC and DMC in order to minimize the possibility of operational bias.

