4.5.4. Procedure at the final analysis

At the time of the final analysis, hypothesis testing for the primary and secondary endpoints will be performed using a weighted combination statistic (Lehmacher and Wassmer 1999; Cui et al. 1999), whereby the Z-statistic from the first stage of the study (the first 120 patients, i.e., 2/3 of the planned information), Z_1 , is combined with the independent Z-statistic from the remaining patients, Z_2 , using prespecified weights $w_1 = \sqrt{0.67}$ and $w_2 = \sqrt{0.33}$ to form a combination statistic $Z^* = w_1 Z_1 + w_2 Z_2$. These weights are used regardless of whether the sample size is increased beyond 180. If $Z^* > 2.5093$, statistical significance is achieved for that endpoint.

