4.8. Efficacy Evaluation

4.6.1 Primary Efficacy Analysis

The primary endpoint is trichotomized PAS on each bolus, determined by VFSS 48 hours (+/- 24 hours) after completion of PES treatment. The three ordinal PAS categories are defined as Safe (PAS 1-3), Penetration (PAS 4-5), and Aspiration (PAS 6-8). Each patient contributes 12 measurements to the primary endpoint, of which six are from boli of a thin consistency and 6 are from boli of a nectar consistency.

The ITT population will be used for the primary analysis.

A cumulative logistic model will be used to analyze the primary endpoint, and a sandwich variance estimator via a generalized estimating equations approach will be used to account for correlated PAS outcomes within each patient.

The statistical model for the primary analysis will include treatment, bolus consistency, baseline maximum PAS, and treatment by consistency interaction as predictors. The response of individual i on bolus t is coded as $y_{it} = 1$ for a safe swallow, $y_{it} = 2$ for a swallow resulting in penetration, and $y_{it} = 3$ for a swallow resulting in aspiration. The log odds of a swallow with response $\leq j$ conditional on predictors x_{it} is modeled as

$$logit(P(y_{it} \le j | x_{it}))$$

$$= \beta_j + \beta_{base} * base_{it} + \beta_{trt} * trt_i + \beta_{nectar} * nectar_t + \beta_{trt*nectar} trt_i * nectar_t$$

with ordered intercept terms $\beta_1 < \beta_2$, a treatment indicator trt_i (1=PES, 0=control), and a consistency indicator $nectar_i$ (1=nectar, 0=thin). The maximum PAS (1-8) of individual i across all pre-treatment swallows of a given consistency at baseline is denoted $base_{it}$. The GEE approach with robust sandwich estimator is used to account for within subject correlation.

Missing PAS data will be imputed in the primary analysis. PAS values that are missing due to application of VFSS stopping criteria will be assigned the worst (highest) post-treatment PAS value. For patients who have no post-treatment PAS data due to lost-to-follow-up or death, the post-treatment PAS values will be imputed from baseline PAS values and other patient baseline characteristics using multiple imputation. In addition, tipping point analysis will be performed as a sensitivity analysis.

The estimated treatment effect in the logistic model will be presented along with standard error. The treatment effect will also be presented as an odds ratio with 95% confidence interval.

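### The SAP tests with an early look and a fixed-weight combination statistic but names no matching estimation method, so the model-based odds ratio and 95% interval need not agree with the test

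*SAP*

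**What the plan says.** **Testing.** SAP 4.3.1 sets formal tests "with all tests conducted at the 1-sided, 0.025 level of significance". SAP 4.5.3 adds a look at 120 patients: "An early efficacy stopping boundary of Z > 2.5093 (one-sided P < 0.0060) will be used for all efficacy endpoints". That value is "derived from the Lan-DeMets O'Brien Fleming spending function at 2/3 information fraction", and the trial stops only if the primary and the secondary endpoint both cross it. If the trial continues, "both endpoints will be tested against the group sequential boundary 1.9929 at the final analysis in a sequential manner".

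SAP 4.5.4 defines the final statistic as Z* = √0.67·Z1 + √0.33·Z2, where Z1 comes from the first 120 patients and Z2 from the rest. "These weights are used regardless of whether the sample size is increased beyond 180". The same section then says that when Z* exceeds 2.5093, "statistical significance is achieved for that endpoint". That conflicts with the 1.9929 in 4.5.3.

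**Reporting.** SAP 4.6.1 presents the logistic-model estimate with its standard error and adds: "The treatment effect will also be presented as an odds ratio with 95% confidence interval". Protocol 9.4.2 leaves modelling details to the SAP. SAP 4.5.5 argues type 1 error control for the combination test. Neither document names a weighted, repeated, bias-adjusted or median-unbiased method.

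**The concern.** The test and the reported interval are built differently in three respects.

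- **Weights.** If the trial grows to 270 patients, the test gives stage 1 a weight of 0.67. A pooled model gives it about 120/270 = 0.44 of the information.
- **Critical value.** A conventional 95% interval uses 1.96. The test uses 1.9929, or 2.5093 as SAP 4.5.4 has it.
- **Selection.** A trial that stops at 120 does so because Z1 was large, so the estimate reported at that point tends to be too high.

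The trial is meant to support a de novo submission (Protocol 4.1), and the odds ratio and its interval are what most readers will use. An estimator chosen after an early stop, or after an interval that contradicts the test, would be post hoc.

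**Working it through.** **1. Reproducing the plan's boundaries.** The inputs are one-sided 0.025 and information fraction 2/3 (SAP 4.3.1, 4.5.3). Spending at 2/3 is 2[1 − Φ(z₀.₉₈₇₅/√(2/3))] = 0.00605, which gives 2.5093. Solving the bivariate normal with correlation √(2/3) gives a final boundary of 1.9929 and overall alpha 0.0250. With 2.5093 at both looks, overall one-sided alpha is about 0.0099. So 1.9929 is the value consistent with the stated 0.025.

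**2. Early stop.** Z1 > 2.5093 always exceeds 1.96, so a 95% interval then excludes 1 and cannot contradict the test. A repeated interval that matches the boundary has level 2Φ(2.5093) − 1 = 98.8%. On the log scale it is 2.5093/1.96 = 1.28 times as wide.

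The documents do not give the information level. Setting fixed-sample power at OR 2.23 to 85% or 95% gives SE(180) = ln 2.23/(1.9929 + z):
- 85%: 0.802/(1.9929 + 1.0364) = 0.265
- 95%: 0.802/(1.9929 + 1.6449) = 0.220

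SE at 120 patients is √1.5 times larger (0.324 and 0.270). The smallest OR that can stop the trial is therefore exp(2.5093 × 0.270) = 1.97 to exp(2.5093 × 0.324) = 2.26.

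Example with Z1 = 2.8:

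| Assumed power | Model OR (95% CI) | Repeated CI | Bias-adjusted OR |
|---|---|---|---|
| 95% | 2.13 (1.25-3.62) | 1.08-4.19 | 2.06 |
| 85% | 2.48 (1.31-4.68) | 1.10-5.59 | 2.38 |

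The bias-adjusted values are of Whitehead type, for a stop on the primary endpoint alone without re-assessment.

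**3. Final analysis with 270 patients**, taking information proportional to patients. Pooled Z = (Z1√120 + Z2√150)/√270.

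| Z1 | Z2 | Z* | Pooled Z | At boundary 1.9929 |
|---|---|---|---|---|
| 2.1 | 0.55 | 2.03 | 1.81 | test significant, 95% CI includes 1 |
| 1.4 | 1.45 | 1.98 | 2.01 | test fails, 95% CI excludes 1 |
| 1.2 | 1.8 | 2.02 | 2.14 | agree; at 2.5093 the test fails and the CI excludes 1 |

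For the last row at the 95% setting, the model OR is 1.47 (1.03-2.09). The weighted estimate is 1.45, with interval 1.004-2.10 at 1.9929 or 0.91-2.31 at 2.5093. Without a sample-size increase, Z = 1.97 already gives an interval above 1 and a failed test at 1.9929.

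**4. Frequencies.** These come from simulation on the log odds ratio scale.
- From the SAP: OR 2.23, DSRS difference 1.75 with SD 4, looks at 120 and 180, maximum 270, both endpoints above 2.5093 to stop.
- Assumed: 1:1 allocation; fixed-sample power 85-95%; endpoint correlation 0-0.6; increase to 270 when conditional power on the primary endpoint is 30-90%; DSRS as the secondary endpoint in the stopping rule, since SAP 4.5.1 ties that endpoint to the ANCOVA.

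| Quantity | True OR 2.23 | True OR 1.5 |
|---|---|---|
| Geometric mean OR if stopped | 2.57-3.03 | 2.29-2.66* |
| Coverage if stopped | not summarised | 73-82%* |
| CI and test disagree, boundary 1.9929 | 0.2-0.6% | about 1.8% |
| CI excludes 1 but test fails, boundary 2.5093 | about 5-10% | about 13-18% |

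*Endpoint correlation 0.3, DSRS effect kept at 1.75.

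At OR 2.23, 22-40% of trials stop early and the OR they report is 15-36% too high. At correlation 0.3 the lower limit lies above the truth in 5-7% of them. Over all trials the mean OR is 2.29-2.33 and coverage is about 94.5-94.8%.

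**The case against.** The strongest reply is that little changes. Significance is judged on Z*, type 1 error is controlled, and over all trials bias and coverage loss are small. All of that stands, and it limits the weight of the point. Several stronger readings also go too far.

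- **A reader might infer that the trial will usually overstate its effect.** The overstatement is conditional on an early stop. Even then it could be diluted, because Protocol 7.3 collects data on everyone enrolled before termination and the ITT population is all randomised patients.
- **A reader might infer that a significant result with an interval including 1 is a common risk.** It cannot occur at an early stop. At 1.9929 it essentially needs a sample-size increase: 0.04-0.2% of trials at OR 2.23 and about 1% at OR 1.5.
- **A reader might infer that the SAP mandates an unadjusted interval with 1.96.** It never says so, and it does not rule out adjustment. The model estimate with its standard error is simply the only estimator it specifies. The restricted Simulation Report is described as holding zone rules, power and type 1 error results, not estimation.
- **A reader might infer that a median-unbiased estimate cures the early-stop case.** The look at 60 is for futility only, so 120 is the first efficacy look. Stage-wise ordering there returns the unadjusted estimate and interval unchanged.

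The frequencies also rest on unseen inputs. Protocol 9.2 and SAP 4.5.3 base re-assessment on both endpoints, while the rule assumed here uses one conditional power. That is why ranges are shown.

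**Conclusion.** The gap is real and worth closing, but it is not a flaw in the test. The plan fixes how significance is decided and leaves open how the effect is estimated once the trial has stopped early or grown. The consequence is material in two situations: an early stop, and a final analysis that applies the 2.5093 in SAP 4.5.4. With 1.9929, disagreement at the final analysis is rare. The boundary conflict therefore drives most of the possible mismatch and has to be settled first.

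The boundary values, interval widths and examples of disagreement follow from the SAP's figures, taking information proportional to patients. The example odds ratios also need an assumed information level, and the frequencies depend on all the assumptions listed with the simulation.

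**What to change.** 1. Reconcile the final boundary between SAP 4.5.3 (1.9929) and SAP 4.5.4 (2.5093).
2. For the final analysis, prespecify the weighted estimate and the interval obtained by inverting the combination test at that boundary.
3. For an early stop, prespecify a repeated interval at 2.5093 (98.8% level) with a bias-adjusted estimate. The repeated interval is centred on the unadjusted estimate, so it does not correct the point estimate. The bias adjustment is modest (2.13 to 2.06 in the example) and will not remove all of the conditional inflation. State whether patients enrolled beyond 120 enter the reported estimate.
4. Keep the model-based odds ratio and 95% interval, labelled as unadjusted.
5. Apply the same method to any DSRS interval that is reported. SAP 4.6.2 plans none, so this does not require a new analysis.

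The cost is one SAP paragraph, with no change to sample size, data collection or conduct. On the log scale the interval is about 28% wider at an early stop. At the final analysis with 1.9929 it is about 2% wider without a sample-size increase (1.9929/1.96 = 1.017). With 270 patients it is about 4% wider: with information in units of that at 180 patients (I1 = 0.667, I2 = 0.833), [1.9929/(√(0.67·I1) + √(0.33·I2))]/[1.96/√(I1 + I2)] = 1.044.

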4.6.2 Secondary Efficacy Analysis

The secondary endpoints are FIOS and DSRS 7 days (+/- 1 day) after completion of investigational treatment.

The ordered categorical endpoint of FIOS will be analyzed by a Cochran-Mantel-Haenszel (CMH) test stratified by site and baseline PAS, using the modified ridit score and test of "row mean scores different" to take into account the ordered nature of the response.

The secondary endpoint of DSRS will be modeled by an ANCOVA model with treatment, center, baseline PAS and baseline DSRS as predictors, and will be tested for statistical significance provided the primary endpoint is found to be statistically significant. The ITT population will be used.

Missing data on the secondary endpoint will not be imputed for the purpose of significance testing.

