8.1.7 FUNCTIONAL ORAL INTAKE SCALE (FOIS)

The FOIS was developed to document the functional level of oral intake of food and liquid in stroke patients with dysphagia³⁰. It is a 7-point ordinal scale that can easily completed by clinicians based on information contained in medical charts, dietary journals, and/or patient reports. Verification of patient reports may be obtained by a spouse or family members or from a variety of sources for institutionalized patients. The FOIS shows strong criterion validity and cross-validation compared with standard clinical measures of stroke outcome. The FOIS has demonstrated sensitivity in expected increase in functional oral intake over a 6-month recovery period in stroke patients. It is completed at the baseline, 7 day, 14-day, and 11-week visits and the data will be entered on the eCRF. Details regarding the administration of the FOIS can be found in the eTMF.

Functional Oral Intake Scale

Level	Description		
1	Nothing by mouth (NPO)		
2	Tube dependent with minimal attempts of food or liquid		
3	Tube dependent with consistent intake of liquid or food		
4	Total oral diet of a single consistency		
5	Total oral diet with multiple consistencies but requiring special preparation or compensations.		
6	Total oral diet with multiple consistencies without special preparation, but with specific food limitations.		
7	Total oral diet with no restriction.		

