9.4.3 ANALYSIS OF THE SECONDARY EFFICACY ENDPOINTS

The secondary efficacy endpoints will be tested for statistical significance sequentially provided the primary endpoint is found to be statistically significant. The ITT population will be used. The first endpoint tested will be FOIS at 7 days following the last investigational treatment. The second endpoint tested will be DSRS at 7 days following the last investigational treatment.

Analysis details are specified in the SAP.

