2. STUDY DESIGN

2.1. Synopsis of Study Design

This is randomized, sham-controlled, patient-masked, outcome assessor-blinded, prospective, multi-center study designed to support a *de novo* submission and FDA clearance for the Phagenesis Phagenyx® System for treatment of oropharyngeal dysphagia following a stroke. The study will follow an adaptive group sequential design with unblinded sample size re-assessment. To ensure 180 evaluable patients with 7-day data and assuming a 20% dropout rate, 225 patients will be enrolled initially. An interim analysis for futility will occur after the first 60 patients complete their 7-day visit and another interim analysis will be performed for efficacy after 120 patients complete their 7-day visit. The total sample size may be increased up to 338 patients after the second interim analysis to ensure 270 evaluable patients. Up to 15 investigational centers across the US and Europe will participate in this study. The enrollment period is expected to be approximately 24 months and patient participation will last for approximately 11 weeks. Patients will be assessed at the following intervals: baseline, within 48 hours of treatment, 7 days, 14 days or at discharge, whichever is first, and 11 weeks after completion of study treatments.

All enrolled patients will have the Phagenyx® Catheter placed and will receive either an active treatment with Pharyngeal Electrical Stimulation or a sham treatment by a HCP who is un-blinded to the treatment assignment.

Randomization will use stratification based on site and baseline PAS. Minimization may also be included to ensure group balance for study site and additional baseline covariates.

[figure not shown]
Administration of all protocol-specific assessments, other than PES or sham treatments, will be conducted by personnel who are blinded to the treatment assignment, including speech pathologists providing standard dysphagia care (excluding VitalStim and e-Stim). The standard dysphagia care data will be collected on the eCRF.

A core laboratory will be established for analysis of all procedural VFSS. The VFSS core lab will provide standardized baseline and follow-up analyses of the primary endpoint as well as VFSS-related tertiary endpoints. Personnel at the VFSS core lab will also be blinded to patient treatment assignment.

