2.2. Study Schema

2.3. Randomization Methodology

Randomization will be stratified by site and baseline PAS. Within each stratum a minimization approach with probabilistic allocation (Pocock and Simon, 1975) will be used to optimize balance between treatment groups on key prognostic factors including NIHSS, baseline PAS, and age. Randomization will occur via the study's EDC system. Administrative permission to access the randomization module and randomization eCRF will be limited to unblinded HCPs who will administer treatment and who will monitor study compliance.

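### FOIS, first in the protocol's secondary testing order, is tested without the baseline FOIS the trial collects: a valid test that gives up power

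*SAP*

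**What the plan says.** **The FOIS test.** SAP 4.6.2 (printed inside section 4.8, with the scale spelled FIOS) reads: "The ordered categorical endpoint of FIOS will be analyzed by a Cochran-Mantel-Haenszel (CMH) test stratified by site and baseline PAS". It uses modified ridit scores and the row-mean-scores statistic. SAP 4.1 gives the same test. Neither place includes a baseline FOIS term.

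**Baseline FOIS is available.** Protocol 8.1.7 says of the scale: "It is completed at the baseline, 7 day, 14-day, and 11-week visits and the data will be entered on the eCRF". The schedules in both documents show it at baseline.

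**Other endpoints use a baseline value.** In the same SAP section: "The secondary endpoint of DSRS will be modeled by an ANCOVA model with treatment, center, baseline PAS and baseline DSRS as predictors". The primary model in SAP 4.6.1 includes baseline maximum PAS. SAP 4.6.3 adjusts continuous exploratory endpoints for their own baselines.

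**The strata.** SAP 2.3: "Randomization will be stratified by site and baseline PAS". SAP 2.1: "Up to 15 investigational centers across the US and Europe will participate in this study". Neither document defines the PAS grouping, and SAP 4.3.3 treats pooling as not applicable.

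**The testing order.** Protocol 9.4.3 tests secondary endpoints in sequence after a significant primary: "The first endpoint tested will be FOIS at 7 days following the last investigational treatment". DSRS comes second. SAP 4.1 and 4.6.2 make DSRS conditional on the primary alone and set no order between FOIS and DSRS.

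**Power.** SAP 4.2 gives 95% for the primary and 85% for both endpoints, the second being DSRS. No effect or power is stated for FOIS.

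**The concern.** A patient's day-7 oral intake depends partly on where the patient started, and patients may enter fed by mouth, nasogastric tube or PEG. A test that ignores the starting level leaves that variation in the noise. Here the starting level is already on the case report form, and the neighbouring endpoint uses its own.

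A second, separate source of loss is the crossing of site with baseline PAS. Ranks are compared only within a stratum, so small strata give few comparisons and a stratum with one arm gives none.

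At stake is the FOIS claim and, under the protocol's order, the DSRS claim behind it. The chance of reaching a DSRS claim in that order cannot exceed the chance of passing FOIS, and the 85% in SAP 4.2 does not include that step.

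**Working it through.** **Inputs from the documents.** Testing is one-sided, with "all tests conducted at the 1-sided, 0.025 level of significance" (SAP 4.3.1). The final boundary is 1.9929 (SAP 4.5.3). SAP 4.5.4 prints 2.5093 as the final threshold, which is the interim value in 4.5.3; 1.9929 is used here. Evaluable patients are 180 of 225, or 270 of 338 (SAP 4.2). Entry needs PAS of at least 4 (Protocol 5.1), so there are at most 5 raw levels if the maximum or qualifying PAS forms the strata. The DSRS difference is 1.75 with SD 4 (SAP 4.2).

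**Step 1: the plan's own figures.**
- 180 / 0.80 = 225, and 270 / 0.80 = 337.5, rounded up to 338. Both match.
- Lan-DeMets O'Brien-Fleming boundaries at information 2/3 are 2.5093 and 1.9929. Both match.
- DSRS at fixed N: 1.75 / 4 = 0.4375, and 0.4375 × √(90/2) = 2.935. Power is Φ(2.935 − 1.9929) = 82.7%, or 83.5% against 1.960. The stated 85% for both endpoints comes from simulations with sample size re-assessment and cannot be reproduced from these documents.
- There is no FOIS figure to reproduce.

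**Step 2: stratum size** = evaluable N / (sites × PAS levels).

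| Layout | N = 180 | N = 270 |
|---|---|---|
| 15 × 2 | 6.0 | 9.0 |
| 15 × 3 | 4.0 | 6.0 |
| 15 × 5 | 2.4 | 3.6 |
| 10 × 2 | 9.0 | 13.5 |

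At 8 × 2 and 180 patients it is 180/16 = 11.25.

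**Step 3: power by simulation.** Assumptions not in the documents:
- latent FOIS effect 0.4375 SD, borrowed from DSRS;
- latent correlation r between baseline and day-7 FOIS of 0.3, 0.5 or 0.7;
- 1:1 allocation balanced within strata, unequal sites, and 20% of 225 patients lost at random;
- seven outcome levels with control-arm shares 30/12/10/16/17/10/5%, and baseline shares 45/15/10/10/12/6/2%;
- no site effect, and one test at N = 180 against 1.9929.

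There were 1,200 trials per row. The Monte Carlo SE near 74% is √(0.74 × 0.26 / 1200) = 1.3 points. The four tests in a row use the same simulated trials.

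| Layout | r | Planned CMH | CMH, PAS strata only | Baseline FOIS, same strata | Baseline FOIS, PAS strata only |
|---|---|---|---|---|---|
| 15 × 2 | 0.3 | 72.7% | 78.3% | 75.0% | 80.4% |
| 15 × 2 | 0.5 | 74.4% | 79.2% | 81.3% | 85.1% |
| 15 × 2 | 0.7 | 73.7% | 79.3% | 87.1% | 94.1% |
| 15 × 5 | 0.3 | 63.4% | 75.3% | 65.9% | 78.7% |
| 15 × 5 | 0.5 | 66.9% | 78.8% | 72.8% | 85.2% |
| 15 × 5 | 0.7 | 64.7% | 77.2% | 80.7% | 92.9% |
| 8 × 2 | 0.3 | 75.6% | 77.9% | 76.8% | 79.8% |
| 8 × 2 | 0.5 | 75.3% | 79.1% | 81.9% | 86.6% |
| 8 × 2 | 0.7 | 76.5% | 79.5% | 91.2% | 94.4% |

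The baseline FOIS columns are rank ANCOVA.

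**Step 4: separate the two losses.**
- *Omitting baseline FOIS* (same strata minus planned). At 15 × 2: 75.0 − 72.7 = 2.3, 81.3 − 74.4 = 6.9 and 87.1 − 73.7 = 13.4 points. At 15 × 5: 2.5, 5.9 and 16.0. At 8 × 2: 1.2, 6.6 and 14.7.
- *Splitting by site* (PAS strata only minus planned). About 5-6 points at 15 × 2, 12-13 at 15 × 5 and 2-4 at 8 × 2.
- *Patients in one-arm strata.* About 2% at 15 × 2, 12% at 15 × 5 and 0.5% at 8 × 2.

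As information, squared ratios of mean Z at 15 × 2 within the same strata are (2.66/2.60)² = 1.05, (2.81/2.61)² = 1.16 and (3.09/2.56)² = 1.46. The approximate ceiling for one baseline covariate, 1/(1 − r²), is 1.10, 1.33 and 1.96.

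**Step 5: validity.** Under the null at r = 0.5, the planned CMH rejected 2.4% (15 × 2) and 3.0% (15 × 5) of 2,500 trials, against 2.3% nominal at 1.9929. The SE is √(0.023 × 0.977 / 2500) = 0.3 points. The first shows no inflation; the second is about 2 SE high and is not clear evidence of it.

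**The case against.** The best defence is that the planned test is sound and conventional. It analyses by the randomization strata, needs no proportional-odds assumption, matches the planned mRS analysis, and is built to pool evidence over many strata. Low power makes the FOIS claim harder to win, not easier. All of this stands. A reader might infer from the thin strata that the test is invalid; Step 5 does not support that.

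The second defence is that the size is unknown. The documents give no FOIS effect, baseline distribution or correlation, fifteen sites is a maximum, and N may rise to 270 evaluable. This also stands. At r = 0.3 the gain from baseline FOIS within the same strata is only 1 to 3 points, and at 8 sites by 2 levels the site split costs little. The simulation has no site effect; a real one would give the site strata some value and shrink that cost further.

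A reader might also set the planned CMH beside a rank ANCOVA with baseline FOIS and no site split, and credit the whole gain to baseline FOIS. That mixes two changes. At 15 × 2 and r = 0.3 the combined information ratio is (2.85/2.60)² = 1.20, above the 1.10 ceiling for baseline adjustment alone.

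Lastly, it is tempting to say that a FOIS miss blocks DSRS. Only Protocol 9.4.3 says so; the SAP conditions DSRS on the primary alone.

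**Conclusion.** The point holds as one of efficiency, not of validity or bias. The first-ranked secondary endpoint omits a baseline measurement that the trial already takes and that the neighbouring endpoint's analysis has a counterpart for.

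Under the stated assumptions at 15 × 2, the omission costs about 2, 7 or 13 power points at correlations of 0.3, 0.5 and 0.7. The site split is a separate cost whose size depends on the undefined PAS grouping and the eventual site count. Both figures are illustrative, because the effect and correlation are assumed. The direction does not depend on the exact values: baseline FOIS helps to the extent that it predicts day-7 FOIS.

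The simulation treats the final analysis as one test. If the combination statistic of SAP 4.5.4 is applied to FOIS, the CMH would be computed on 120 and then 60 patients without a sample size increase. At 15 × 2 the second stage has 60/30 = 2 patients per stratum. That further loss is not in the figures above.

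Whether a FOIS miss also costs the DSRS claim cannot be settled until the two documents agree on the order.

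**What to change.** In SAP 4.1 and 4.6.2, make the confirmatory FOIS test a rank ANCOVA, or a proportional-odds model, with baseline FOIS, baseline PAS and site. Keep the stratified CMH as a sensitivity analysis. Adjusting for NIHSS and age, the other minimization factors, is optional.

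In the same edit:
- define the baseline PAS grouping and say how small sites are handled;
- state one testing order for FOIS and DSRS in both documents;
- align SAP 4.3.4, which says no covariate-adjusted analysis is planned, and SAP 4.6.3, which also lists 7-day FOIS as exploratory.

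The cost is SAP wording, with no new data, visits or patients. The change should be settled before the first unblinded interim analysis. The only downside is a check of proportional odds if that model is chosen; rank ANCOVA avoids it and stays close to the planned test.
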